3.5 Intervention Arms

# Facilitated advance care planning arm

Participants randomized to the facilitated ACP arm will participate in Respecting Choices®, a facilitated ACP conversation designed for adults with chronic incurable illness. Conversations are led by a nurse or social worker with supportive oncology experience who has been trained as a Respecting Choices® facilitator. Each patient will participate in up to three face-to-face, video, or telephonic visits, lasting 45-60 minutes each. The facilitator initiates contact with a call to each patient to establish rapport, determine the preferred visit mode, schedule the visit, and facilitate overall intervention participation. Visits will include the patient's medical decision maker (health care agent), when available, and any other members of the family and/or caregivers the patient wishes to include. Visits will be held in a private location (oncology clinic, patient's home, or research office) and audio-recorded for fidelity monitoring. During the ACP conversation visit, facilitators will use the "First Steps® ACP Conversation Guide: Adults with Chronic Illness" structured interview tool as a discussion roadmap and provide guidance in choosing a medical decision maker, exploring serious illness understanding and experiences, identifying goals and values, and making future treatment decisions. Facilitators will provide a copy of the AD used throughout UPMC, assist with completion and uploading to the patient's electronic medical record, when appropriate, and make recommendations for communicating goals and sharing written preferences.

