# 5.2 Primary and Secondary Outcomes

All analyses for treatment group comparisons will use an intention-to-treat approach.

The primary outcome is ACP engagement. We will test the effect of treatment assignment on the primary outcome using linear mixed models. The model will include treatment group, and baseline ACP engagement as fixed effects. To adjust for possible clustering of patients seen by the same facilitator or provider, we will include random effects for facilitators (for patients in the facilitated ACP group only) and oncologists.

The same analytic approach will be used for secondary outcomes: perceived quality of EOL care and caregiver symptoms of anxiety, depression and PTSD. Binary outcomes such as ACP discussions, AD completion, documented care goals, and receipt of goal-concordant EOL care will be compared using mixed effect logistic regression with the same set of fixed effects and random effects as in the models for continuous outcomes. We will also compare the rates of completion of intervention between the two intervention groups, using the same model as for other binary outcomes.

Analyses of health care utilization data will use GLMM (generalized linear mixed model), with logit link (binary distribution) for dichotomous (yes/no) health care outcomes such as chemotherapy within last 2 weeks of life. Again, we will use intervention group and baseline ACP as fixed effects and oncologist and clinic as random factors.

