#### 5.5 Sample Size and Power Calculations

We selected our sample size to provide ample power to assess differences in the primary outcome—ACP engagement—as well as secondary patient, caregiver, and healthcare utilization outcomes. All calculations were conducted using  $\alpha$ =0.05, based on two-sample t-tests for continuous outcomes and chi-squared tests for binary outcomes. To adjust for possible clustering effect within each oncologist, we used the design effect (DE=1+[(1+CV²)m-1)] $\rho$ ), where CV=the coefficient of variation for cluster size and m=the number of patients per oncologist. Conservatively estimating a 25% loss

to follow-up for patient-reported outcomes, our sample size will provide >98% power to detect a moderate effect size (Cohen's d=0.5) in our primary outcome—ACP engagement. While any increase in ACP engagement may be associated with clinically meaningful improvements in EOL outcomes, a minimal clinically important difference has not been established. A moderate effect size (0.35 on a 5-point score, based on a SD of 0.7),27 ensures that we will be able to detect a difference comparable to the changes seen with ACP interventions in prior trials. We will have >78% power to detect a 15% difference in rates of ACP discussions with family and physicians between groups (assuming discussion rates of 25% in the web-based arm) and >99% power to detect a 20% difference in rates of AD completion (assuming an AD completion rate of 50% in the web-based ACP arm). Power is similarly adequate for all caregiver-reported outcomes, assuming a 75% caregiver participation rate and 15% loss to follow-up, which results in an effective sample size of 254. For caregiver-reported quality of EOL care we will have 97.6% power to detect a moderate effect size, and for caregiver anxiety and depression we will have 83.2% power to detect a clinically meaningful difference (Cohen's d=0.368).59 Anticipating that 90% of patients will die during the study period (resulting in an effective sample size of 360), we will have >73-78% power to detect an 8% absolute decrease in ICU admissions and chemotherapy use at the EOL and >80% power to detect a 15% decrease in no hospice or hospice ≤ 3 days before death, based on national data.

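### Section 5.2 omits the facilitator random effect only from the Aim 2 utilization models, without a stated reason; if facilitators differ, those secondary tests run modestly above 5%

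*Combined protocol and SAP*

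**What the plan says.** Section 5.2 specifies the random effects model by model.

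- **Primary outcome (ACP engagement):** "To adjust for possible clustering of patients seen by the same facilitator or provider, we will include random effects for facilitators", limited to patients in the facilitated arm, plus oncologists.
- **Continuous secondary outcomes** (perceived quality of end-of-life care; caregiver anxiety, depression and PTSD symptoms): the same approach as the primary.
- **Binary Aim 1 outcomes:** mixed-effects logistic regression "with the same set of fixed effects and random effects as in the models for continuous outcomes".
- **Completion of the intervention:** "using the same model as for other binary outcomes".
- **Healthcare utilization (Aim 2):** generalized linear mixed models with a logit link for the yes/no outcomes. "Again, we will use intervention group and baseline ACP as fixed effects and oncologist and clinic as random factors".

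The last item is the only one without facilitators, and the only one with clinic. No section explains either difference. Section 3.6 randomizes 1:1 at the patient level. Section 3.5 describes visits led by a trained facilitator, in the facilitated arm only.

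**The concern.** The reason section 5.2 gives for the facilitator term is that patients seen by the same facilitator may have correlated outcomes. That reason applies equally to end-of-life utilization, because the same facilitators hold the same conversations with the patients whose chemotherapy, ICU, hospital and hospice use is later counted. The sentence begins with a word that signals repetition, yet the list of random effects differs. This may be a drafting slip.

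Patient-level randomization spreads each clinic and each oncologist over both arms, so their effects largely cancel from the arm comparison. Facilitator effects sit in one arm only and do not cancel. If they exist and the model ignores them, the standard error of the arm effect is too small and the confidence interval too narrow. Readers would also see Aim 1 results that allow for facilitators beside Aim 2 results that do not.

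**Working it through.** **Inputs from the documents (section 5.5):** 400 patients, 90% expected to die, nominal alpha 0.05. 400 × 0.90 = 360, which matches "resulting in an effective sample size of 360". With 1:1 allocation this is about 180 per arm.

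**Assumptions, not in the documents:** number of facilitators K = 4 to 8; facilitator ICC 0 to 0.01; event rate 13%. The plan states that "we will have >73-78% power to detect an 8% absolute decrease in ICU admissions and chemotherapy use at the EOL" but gives no base rates. A fall from 13% to 5% with 180 per arm gives 75.8% power by the two-proportion formula, inside the stated range, so 13% is a workable base rate.

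**What the ICC means.** The between-facilitator SD is √(ICC × 0.13 × 0.87). This is 2.4 percentage points at ICC 0.005 and 3.4 points at 0.01. Against a planned effect of 8 points, 0.01 is treated as the upper working value.

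**Formula.** With m = 180/K patients per facilitator:

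- design effect in the facilitated arm: DE = 1 + (m − 1) × ICC
- true over assumed variance of the arm difference: R = (1 + DE)/2, because only one arm is clustered
- true two-sided error = 2 × [1 − Φ(1.96/√R)]

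Example, K = 4 and ICC 0.01: m = 45; DE = 1 + 44 × 0.01 = 1.44; R = 1.22; 1.96/√1.22 = 1.775; error 7.6%.

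| ICC | K = 4 | K = 6 | K = 8 |
|---|---|---|---|
| 0 | 5.0% | 5.0% | 5.0% |
| 0.005 | 6.28% | 5.84% | 5.62% |
| 0.01 | 7.60% | 6.70% | 6.25% |

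Outside the 4-8 range, at ICC 0.01, the formula gives 8.5% for K = 3 and 5.8% for K = 12.

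**Simulation check.** Logistic data with facilitator effects in one arm, clinic and oncologist left out, 15,000 runs per cell, model without the facilitator term: 5.4%-6.0% at ICC 0.005 and 6.3%-7.3% at 0.01.

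**Do clinic and oncologist absorb it?** The planned structure was simulated with 6 clinics, an assumed 24 oncologists, an assumed logit SD of 0.2 for each, and baseline ACP omitted (4,000 runs per cell, Monte Carlo SE about 0.4 points). With K = 4 the error was 4.2% at ICC 0, 5.6% at 0.005 and 7.4% at 0.01. At ICC 0.01 it was 7.1% when facilitators were tied to clinics. With K = 6 and ICC 0.01 it was 6.2% (6.4% tied). Clinic and oncologist effects do not replace the missing term.

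**Effect of adding the term** (maximum likelihood, Wald z, clinic and oncologist left out), K = 4/6/8:

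- error: 4.1/4.2/4.1% at ICC 0; 4.9/4.6/4.4% at 0.005; 5.7/4.9/4.9% at 0.01. A separate rerun for K = 4 at ICC 0.01 gave 6.3%.
- power for 13% against 5%, without then with the term, at ICC 0: 76.4 to 71.8%, 76.3 to 72.1%, 76.1 to 71.4%
- the same at a logit SD of about 0.3 (the ICC 0.01 spread): 72.8 to 65.9%, 73.4 to 67.4%, 73.4 to 68.1%

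**The case against.** The strongest case for leaving the model alone has three parts.

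**The size rests on assumptions.** The documents give neither K nor the ICC, and 7.6% is the top corner of the assumed grid. Facilitators are certified, use a common interview guide, have every session recorded and are scored monthly on a sample of sessions (sections 3.5 and 3.8), which should limit differences between them. At ICC 0.01 with no average effect, facilitators two SDs either side of the mean would move utilization by about 6.7 points (2 × 3.36) in opposite directions, close to the whole planned effect. This stands, and is why the result is given as a range starting at 5%.

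**The inflation concerns one kind of null.** If facilitated ACP changes no patient's utilization, facilitators cannot differ through it and the test is nominal. The excess arises when effects vary by facilitator but average to zero. This also stands, but inference about the average over facilitators is what section 5.2 chooses for its other outcomes.

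**The term costs power and corrects imperfectly.** With K = 4 and ICC 0.01 the facilitator variance is estimated at zero in 57% of runs, which returns the current model. A team could weigh this and omit the term, but section 5.2 shows no sign of that choice.

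Two stronger readings are tempting. A reader might infer that the trial ignores facilitator clustering, or that its primary result is at risk. Section 5.2 rules this out, since the primary model includes the term. A reader might also take section 5.5, which says "To adjust for possible clustering effect within each oncologist, we used the design effect", as further evidence. That sentence concerns planning power, not the utilization analysis model, and does not bear on the omission.

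**Conclusion.** The concern holds as an unexplained inconsistency confined to the Aim 2 utilization models. The direction is known: for any positive facilitator ICC the planned tests run above 5%. The size is modest, about 5.6%-6.3% at ICC 0.005 and 6.3%-7.6% at 0.01, and there is no inflation at ICC 0. These figures rest on 180 deaths per arm, which follows from section 5.5, and on 4 to 8 facilitators and the ICC values, which are assumptions. A reader might infer that the utilization tests will in fact run at 7.6%; the documents do not support any single figure. Nor do these results make a small-sample t reference a requirement: in these models it would cut power to 39%-60%, depending on K and the spread. This should be corrected, as a consistency fix for secondary outcomes.

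**What to change.** In section 5.2, add to the utilization models the facilitator random effect for facilitated-arm patients only, as in the other models, and keep oncologist and clinic. Web-based patients carry no facilitator effect.

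Under intention to treat, code each facilitated-arm patient to the assigned facilitator, including patients who never have a visit. Section 3.5 offers a basis: "The facilitator initiates contact with a call to each patient to establish rapport". Section 3.8 also mentions scheduling calls but does not say who makes them, so the assigned facilitator should be recorded for every patient in that arm.

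The cost is one model term and a line of SAP text, with no extra patients. For an 8-point drop from an assumed 13%, power falls from about 76% to 71%-72% if facilitators do not differ, a loss of 4-5 points. At the ICC 0.01 spread the loss is 5-7 points, from about 73% to 66%-68%. With few facilitators the correction is only partial: for K = 4 at ICC 0.01 the error falls from about 7.3% to 5.7%-6.3%. If the omission was deliberate, a stated reason would remove the inconsistency but leave the error rates unchanged.

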### 5.3 Handling of Missing Values

We will prevent and monitor missing data by using an eSYSDM, which will automatically produce an error message notifying the user that the field must be completed when required fields are left blank. The eSYSDM also performs important tracking duties by monitoring screening information, eligibility status, follow-up interviews due, and study group assignment to ensure that the required data collection instruments are administered within the time constraints dictated by the study protocol. We will compare baseline characteristics between patients with complete follow-up to those without by randomization group, in order to assess potential biases that may exist in the complete case analysis. We will also record and report all reasons for study drop-out using a withdrawal/termination form to assess the missing data mechanism (missing completely at random, missing at random, or non-ignorable missingness, meaning the data missingness is related to the actual value). We will conduct sensitivity analyses for primary and secondary outcomes using several validated methods: (1) complete case analyses, which assumes missing completely at random; (2) multiple imputation using M=10 imputations, which assumes missing at random; and (3) assigning poor scores and good scores for missing values differentially by treatment group, which aligns with non-ignorable missingness.

#### 5.4 Interim & Final Analyses

We will not have any planned interim looks for stopping for efficacy. The final analyses will be conducted once study follow-up is complete, after all data is cleaned and the study database is locked.

#### 5.5 Sample Size and Power Calculations

We selected our sample size to provide ample power to assess differences in the primary outcome—ACP engagement—as well as secondary patient, caregiver, and healthcare utilization outcomes. All calculations were conducted using  $\alpha$ =0.05, based on two-sample t-tests for continuous outcomes and chi-squared tests for binary outcomes. To adjust for possible clustering effect within each oncologist, we used the design effect (DE=1+[(1+CV²)m-1)] $\rho$ ), where CV=the coefficient of variation for cluster size and m=the number of patients per oncologist. Conservatively estimating a 25% loss

to follow-up for patient-reported outcomes, our sample size will provide >98% power to detect a moderate effect size (Cohen's d=0.5) in our primary outcome—ACP engagement. While any increase in ACP engagement may be associated with clinically meaningful improvements in EOL outcomes, a minimal clinically important difference has not been established. A moderate effect size (0.35 on a 5-point score, based on a SD of 0.7),27 ensures that we will be able to detect a difference comparable to the changes seen with ACP interventions in prior trials. We will have >78% power to detect a 15% difference in rates of ACP discussions with family and physicians between groups (assuming discussion rates of 25% in the web-based arm) and >99% power to detect a 20% difference in rates of AD completion (assuming an AD completion rate of 50% in the web-based ACP arm). Power is similarly adequate for all caregiver-reported outcomes, assuming a 75% caregiver participation rate and 15% loss to follow-up, which results in an effective sample size of 254. For caregiver-reported quality of EOL care we will have 97.6% power to detect a moderate effect size, and for caregiver anxiety and depression we will have 83.2% power to detect a clinically meaningful difference (Cohen's d=0.368).59 Anticipating that 90% of patients will die during the study period (resulting in an effective sample size of 360), we will have >73-78% power to detect an 8% absolute decrease in ICU admissions and chemotherapy use at the EOL and >80% power to detect a 15% decrease in no hospice or hospice ≤ 3 days before death, based on national data.

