# 3. STUDY DESIGN

The study is a single-blind, patient-level randomized trial, using mixed methods to compare the effectiveness of facilitated ACP versus web-based ACP among 400 patients with advanced cancer and their caregivers.

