#### 3.6 Randomization Procedures

Upon completion of baseline patient and caregiver interviews, patient-caregiver pairs will be randomized 1:1 at the patient level to receive either the facilitated ACP or the web-based ACP intervention. We chose patient-level randomization, consistent with most prior ACP trials, because both interventions are at the patient level and do not involve clinician- or system-level changes. The risk of contamination is extremely low because both interventions will be conducted in private and are unlikely to influence systematic changes in physician practices. To further ensure against any potential contamination, we will ask enrolled participants and caregivers not to discuss either intervention with other patients or caregivers once they are told which group they have been randomized to.

The randomization sequence will be generated by the lead statistician who will not be involved in study recruitment or treatment allocation. The statistician will use R (R Foundation for Statistical Computing, Vienna, Austria) to generate a randomization sequence that will be fed into the webbased database portal, so that each patient-caregiver pair will be randomly assigned to a group upon completion of their baseline interview.

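### The power of more than 99% stated for a 20-point difference in AD completion is not attainable: it is about 94.6% after the plan's own 25% loss, and 98.5% even with all 400 patients and no clustering

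*Combined protocol and SAP*

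**What the plan says.** Section 3 sets out to "compare the effectiveness of facilitated ACP versus web-based ACP among 400 patients with advanced cancer and their caregivers", and Section 3.6 says "patient-caregiver pairs will be randomized 1:1 at the patient level", so there are 200 patients per arm.

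Section 5.5 gives alpha as 0.05, with calculations "based on two-sample t-tests for continuous outcomes and chi-squared tests for binary outcomes". It says that a design effect for clustering within oncologist was used, but gives no values for the coefficient of variation, the cluster size or the intracluster correlation. It assumes a 25% loss to follow-up for patient-reported outcomes, which leaves 300 evaluable patients.

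Two binary patient outcomes then share one sentence. The first reads "We will have >78% power to detect a 15% difference in rates of ACP discussions", from 25% in the web-based arm. The second is the AD completion claim: ">99% power to detect a 20% difference in rates of AD completion (assuming an AD completion rate of 50% in the web-based ACP arm".

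On measurement, the outcome table in Section 4.3 assesses AD completion by a single patient question at baseline and 12 weeks, and describes medical record review as additional. The text of the same section names both sources.

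**The concern.** A 20-point difference centred near 60% is large, but 150 or even 200 patients per arm looked too few to bring the type II error below 1%. The neighbouring figure for ACP discussions is only just above 78%, and a step from that to above 99% on the same patients is more than the change in rates seemed able to explain.

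At stake is the accuracy of the sample-size section for a named Aim 1 secondary outcome. The plan implies that a true 20-point difference would be missed less than once in a hundred trials. If the real risk is several times that, readers are misinformed about what the trial can show on AD completion. They also cannot recover the figure, because the section gives no sample size, data source or design effect for it.

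**Working it through.** **Inputs.** 400 patients, 1:1 (Sections 3 and 3.6); 25% loss, so 150 per arm (Section 5.5); 50% versus 70%, alpha 0.05, chi-squared (Section 5.5). Sidedness is not stated and is inferred in step 1. The design effect (DE) is not given, so DE = 1 is taken as the most favourable case.

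**Formula.** With p̄ the mean of p₁ and p₂, and n per arm:

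power = Φ{ [ |p₁ − p₂| − z·√(2p̄(1 − p̄)/n) ] / √([p₁(1 − p₁) + p₂(1 − p₂)]/n) }, z = 1.96 two-sided. Clustering replaces n by n/DE.

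**Step 1. Find the basis of the section's other figures.**
- Caregiver anxiety and depression, d = 0.368, 254 caregivers (127 per arm), stated 83.2%: the t-test gives 83.2% two-sided and 90.0% one-sided. The plan is therefore testing two-sided.
- Primary outcome, d = 0.5, stated above 98%: 150 per arm gives 99.1%.
- ACP discussions, 25% versus 40%, stated above 78%: at 150 per arm, (0.15 − 0.1060)/0.0534 = 0.824, so power is 79.5%. At DE = 1.04 it is 77.9%, so the stated figure allows a design effect of at most about 1.04. With 200 per arm it would be 89.6%.

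These fit two-sided tests with 300 evaluable patients for patient-reported outcomes and little clustering.

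**Step 2. AD completion, 50% versus 70%, p̄ = 0.60.**
- 150 per arm: √(0.48/150) = 0.05657, times 1.96 = 0.1109; √(0.46/150) = 0.05538. (0.2 − 0.1109)/0.05538 = 1.609, so power is **94.6%**.
- 200 per arm: √(0.48/200) = 0.04899, times 1.96 = 0.0960; √(0.46/200) = 0.04796. (0.2 − 0.0960)/0.04796 = 2.168, so power is **98.5%**.
- With DE = 1.04: 93.8% at 300 patients and 98.2% at 400.

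**Step 3. Does the choice of method matter?** Two-sided power for 50% versus 70%, DE = 1:

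| Method | 150 per arm | 200 per arm |
|---|---|---|
| Pooled chi-squared | 94.6% | 98.5% |
| Unpooled variance | 95.1% | 98.7% |
| Arcsine | 94.6% | 98.4% |
| Continuity-corrected | 93.2% | 98.1% |
| Exact enumeration | 94.7% | 98.4% |

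No two-sided entry exceeds 98.7%. A fall from 50% to 30% gives the same power as a rise to 70%. Reading the 20% as relative (50% to 60%) gives 41% to 52%. One-sided, the figures are 97.3% at 300 patients and 99.4% at 400.

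**Step 4. What 99% would take.** n = (1.960·√0.48 + 2.326·√0.46)² / 0.2² = (1.358 + 1.578)² / 0.04 ≈ 215.5, so 216 per arm, 432 evaluable in total. With 25% loss that is 432/0.75 = 576 randomised. With 150 per arm, 99% power corresponds to a difference of about 24 points (50% versus 73.7%). With 200 per arm it corresponds to just under 21 points.

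**The case against.** The strongest reply concerns the data source. The 25% loss is stated for patient-reported outcomes, and Section 4.3 says AD completion will also be assessed from medical records, which Section 3.9 assigns to blinded staff and which needs no 12-week interview. If the records serve for all 400 patients, power is 98.5%, about half a point short of the claim, and the two figures in the sentence could rest on different sample sizes. This stands in part. The outcome table puts the patient question first and the records second, Section 5.5 does not exempt AD completion from the loss, and the documents do not settle the matter. It reduces the gap but does not close it, since 98.5% is still below 99% before any clustering.

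The figure for ACP discussions is a lower bound, so it points to 300 patients without proving it. That is fair. However, two-sided testing with 400 patients and no clustering meets the bound for discussions (89.6%) and still fails the one for AD completion, so no two-sided basis within the trial's size satisfies both.

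Section 5.5 does not state sidedness, and a one-sided test with no loss and no clustering gives 99.4%. That route conflicts with the 83.2% caregiver figure, which reproduces only two-sided.

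Finally, about 94% is ample for a secondary outcome, the plan sets no hierarchy that would make this outcome decisive, and a null result would be judged by its estimate and interval. All of that is right, and it limits the consequence to a misreported figure.

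**Conclusion.** The concern holds. Two-sided power for 50% versus 70% is 94.6% with 300 evaluable patients and at most 98.5% (98.7% by the most favourable approximation) with all 400, so the stated value above 99% is not met on either reading of how AD completion is measured.

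At 300 patients the type II error is 5.4% with no clustering and about 6.2% at a design effect of 1.04, the largest value compatible with the plan's own figure for ACP discussions. That is at least five times the implied maximum of 1%. On the medical-record reading with 400 patients it is about 1.5%.

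The conclusion rests on two-sided testing, inferred from the caregiver figure, and on the 20% being an absolute difference, which is the reading more favourable to the plan. The size of the gap, though not its existence, depends on whether the 25% loss applies to AD completion. The sample size and the primary-outcome power are unaffected.

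**What to change.** Correct the figure in Section 5.5 in one of three ways:

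- If the 12-week patient question defines AD completion, state about 94% power for 50% versus 70% with 300 evaluable patients.
- If medical records in all 400 patients define it, say so, align Section 4.3, and state about 98%.
- If 99% is to be kept with 300 evaluable patients, state the difference as about 24 points.

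In each case give the sample size, the sidedness of the test and the design-effect inputs, so that the figure can be reproduced. The cost is an edit to one sentence and a slightly less favourable stated power. No change to enrolment, design or analysis follows.

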#### 2. AIMS AND OBJECTIVES

The purpose of this study is to compare the effectiveness and implementation costs of two different patient-facing ACP interventions among patients with advanced cancer and their caregivers: (1) facilitated ACP using the Respecting Choices® model versus (2) web-based ACP using the PREPARE online ACP tool. The study includes longitudinal outcomes that define successful advance care planning based on a recent international consensus panel and incorporates a qualitative evaluation to identify factors that influence ACP effectiveness.

Aim 1 will compare the effectiveness of facilitated ACP versus web-based ACP on patient and family caregiver outcomes. Using a validated, patient-reported measure, we will compare the interventions' impact on ACP engagement at 12 weeks (1° outcome), ACP discussions with caregivers and clinicians, advance directive (AD) completion, and caregiver symptoms of depression and anxiety. For patients who die during the study period, we will use validated, caregiver-reported measures to compare perceived quality of EOL care, patients' EOL goal attainment, and bereaved caregiver symptoms of depression, anxiety, and post-traumatic stress.

Aim 2 will assess implementation costs and the effects of facilitated ACP and web-based ACP on healthcare utilization at end of life. To inform future dissemination efforts and aid in understanding optimal financing models, we will calculate implementation costs of each intervention and determine effects on healthcare utilization at EOL, including hospitalizations, chemotherapy use, and hospice use.

Aim 3 will identify contexts and mechanisms that influence the effectiveness of facilitated ACP versus web-based ACP. We will conduct a qualitative evaluation, using in-depth interviews with patients, caregivers, and clinicians, and perform thematic analysis to understand for whom, how, and in what circumstances facilitated ACP versus web-based ACP are most effective.

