Receipt of goal- concordant EOL care	Two validated caregiver-reported questions have been used to measure receipt of goal-concordant EOL care for patients with cancer: (1) "In your opinion, to what extent were [the patient's] wishes followed in the medical care received in the last month of life?"; and (2) Caregivers asked about patient's preferred and actual places of death, with questions separated in the survey to minimize conscious comparison. 	Bereavement
Quality of EOL care	The Caregiver Evaluation of Quality of End-of-Life Care (CEQUEL) scale is a 13- item instrument (range of scores 13-26) with demonstrated reliability and convergent validity among cancer caregivers. Strengths include brevity and clinical relevance, with inclusion of 4 distinct but related factors (prolongation of death, perceived suffering, shared decision-making, and preparation for death) associated with caregiver bereavement outcomes. 	Bereavement

Depression and anxiety symptoms	Hospital Anxiety and Depression Scale (HADS) is a widely-used 14-item instrument measuring symptoms of depression and anxiety. $^{33}$ It has been extensively validated for screening emotional distress among advanced cancer patients $^{34}$ and family members. $^{35}$ Score of $\geq$ 8 on either domain indicate significant symptoms of depression or anxiety with good sensitivity and specificity. $^{36}$	Baseline, 12 weeks, Bereavement
Post-traumatic stress symptoms	Impact of Events Scale is a 22-item self-report instrument for PTSD symptoms with 3 subscales measuring intrusion (8 items), avoidance (8 items) and hyperarousal (6 items). Subscales have high internal consistency (Cronbach's alpha ranging from 0.79-0.92). A score of 30 or higher is considered a clinically significant burden.	Bereavement

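### Section 5.5 uses one caregiver sample of 254 for every caregiver outcome, but quality of end-of-life care is measured only after a death; the plan's own 90% death rate gives about 229.

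*Combined protocol and SAP*

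**What the plan says.** Section 5.5 makes one statement for the whole class of caregiver outcomes: "Power is similarly adequate for all caregiver-reported outcomes, assuming a 75% caregiver participation rate and 15% loss to follow-up". The resulting figure is attached at once to an end-of-life outcome: "which results in an effective sample size of 254. For caregiver-reported quality of EOL care we will have 97.6% power", for an effect called moderate. The same sentence gives 83.2% power at d = 0.368 for caregiver anxiety and depression, with no time point. The next sentence, on healthcare utilization, brings in mortality: "Anticipating that 90% of patients will die during the study period (resulting in an effective sample size of 360").

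Section 2 limits the end-of-life measures to decedents: "For patients who die during the study period, we will use validated, caregiver-reported measures to compare perceived quality of EOL care". The outcome table in Section 4.3 agrees, listing bereavement as the only time point for the quality of end-of-life care scale (CEQUEL). The anxiety and depression scale (HADS) is scheduled at three: "Baseline, 12 weeks, Bereavement".

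On clustering, Section 5.5 says: "To adjust for possible clustering effect within each oncologist, we used the design effect". It gives the formula but no values for the coefficient of variation, the number of patients per oncologist or the intraclass correlation.

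**The concern.** A caregiver can rate end-of-life care only if the patient has died during the study. The base for that outcome therefore needs three factors: death, caregiver participation and retention. The figure of 254 uses only the last two, although the plan's death rate stands in the following sentence. Outcomes with different denominators have been given the same one.

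Two things are at stake, both confined to secondary outcomes. The sample size and power stated for quality of end-of-life care are higher than the plan's own rates support. And because HADS is measured both at 12 weeks and at bereavement, a reader may take the unlabelled 83.2% to cover both. Post-traumatic stress and goal-concordant care share the bereavement base and have no stated power of their own.

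**Working it through.** **Inputs**

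- 400 patients (Section 3), allocated 1:1 (Section 3.6).
- Caregiver participation 75%, loss to follow-up 15%, deaths 90% (Section 5.5).
- Two-sample t-test at alpha 0.05 (Section 5.5). Sidedness is not stated. Two-sided is used here because it reproduces the 83.2%; one-sided (normal approximation) would give 90.1%.
- d = 0.368 for anxiety and depression (Section 5.5).
- d = 0.5 for quality of end-of-life care. This is an assumption: Section 5.5 equates moderate with 0.5 only for the primary outcome.

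**Step 1. Reproduce the plan's sample size.** 400 x 0.75 x 0.85 = 255. Rounding down within arms gives 127 per arm, or 254. No term for death is present.

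**Step 2. Reproduce the plan's power.** At N = 254 with no design effect, power is 97.8% at d = 0.5 (stated 97.6%) and 83.2% at d = 0.368 (stated 83.2%). So 254 is the base behind the stated figures, to within 0.2 points.

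**Step 3. Apply the plan's death rate.** If death, participation and loss are independent:

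400 x 0.90 x 0.75 x 0.85 = 229.5

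This is 255 - 229.5 = 25.5 fewer caregivers, or 10%.

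**Step 4. Ask what would rescue 254.** Participating caregivers of patients who die number 400 x 0.90 x 0.75 = 270. Keeping 254 of them means retention of 254/270 = 0.941, a loss of 5.9% rather than 15%.

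**Step 5. Bound the dependence.** With 360 deaths and 255 retained caregivers among 400 patients, the overlap is at least 360 + 255 - 400 = 215 and at most 255.

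| Caregiver base | Power at d = 0.5 | Power at d = 0.368 |
|---|---|---|
| 254 (as stated) | 97.8% | 83.2% |
| 229.5 (independence) | 96.5% | 79.3% |
| 215 (lower bound) | 95.4% | 76.6% |
| 255 (upper bound) | 97.8% | 83.3% |

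The difference detectable with 83.2% power moves from d = 0.368 at N = 254 to d = 0.387 at N = 229.5.

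**Step 6. Check the design effect.** Allowing for rounding, 83.2% at d = 0.368 requires an effective N of 253.8 to 254.5, which is a design effect of 1.00 on 254. At d = 0.5, 97.6% requires 248.9 to 251.1, a design effect of 1.01 to 1.02. No single design effect gives both figures at d = 0.5; the 97.6% fits N = 254 if d is about 0.496. Either way, the 83.2% shows no clustering adjustment. As illustration only, since the plan gives no inputs, design effects of 1.1 to 1.3 at N = 229 would give about 95% to 91% at d = 0.5 and 75% to 68% at d = 0.368.

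**The case against.** The strongest reply is that almost nothing changes. Quality of end-of-life care keeps at least 95.4% power even at the lower bound, so calling its power adequate remains fair. That stands, and it sets the weight of this point.

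Second, 229 is not forced by the text. The 15% loss is not defined, and if it already counts caregivers of patients still alive at study end, the base returns to about 255. This is possible, but it implies only about 6% true loss among bereaved caregivers, and Section 5.5 would need to say so. The base could also be lower than 229, because deaths late in the study may leave no time for an interview 12 weeks or more afterwards.

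Third, Section 2 lists caregiver depression and anxiety separately from the bereaved caregivers' symptoms, so the 83.2% can be read as a 12-week figure. On that reading it is correct, and 79% corrects no printed number; nor does it breach a threshold, since the same section accepts 73-78% for other outcomes. But the wording does not settle the time point. Section 4.3 schedules HADS at both, Section 5.2 describes post-traumatic stress simply as a caregiver symptom although it is measured only at bereavement, and the opening claim in Section 5.5 covers all caregiver-reported outcomes.

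Fourth, the missing design-effect inputs are a separate matter and would not justify a comment alone. That is fair; they are included here because the same sentences need rewriting.

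**Conclusion.** The concern holds. The 254 omits the death condition that defines the bereavement outcomes, although the plan states the death rate one sentence later. Under independence the bereavement base is about 229. Power for quality of end-of-life care falls by about one point (97.6% to 96.5%, assuming d = 0.5). Power for HADS at bereavement is about 79% at d = 0.368, against an unlabelled 83.2% that is right for 12 weeks.

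If independence fails, the base lies between 215 and 255, and the powers between 95.4% and 97.8% and between 76.6% and 83.3%. These figures carry no allowance for clustering, and any design effect above 1 lowers them. The correction is minor and leaves the primary outcome, the sample size and the planned analyses as they are.

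**What to change.** In Section 5.5:

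- Give two caregiver bases: about 254 at 12 weeks and about 229 at bereavement. State that the second assumes death, participation and loss are independent, and say whether the 15% loss includes caregivers of surviving patients.
- Restate power for quality of end-of-life care as about 96%, and print the value of d used.
- Label 83.2% as the 12-week HADS figure and add about 79% for HADS at bereavement.
- Either apply the design effect to the 83.2%, stating the coefficient of variation, patients per oncologist and intraclass correlation, or say that none was applied.

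The cost is two or three sentences and a few figures. Stated power for the bereavement outcomes becomes slightly less favourable, and the design does not change.
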